#### Recruitment

Recruitment will be face to face and babies will be enrolled following admission to the Neonatal Intensive Care Unit. It is likely that most babies will have previously had an PIVC for treatment or fluids. The study will be advertised on posters within the Neonatal Intensive Care Unit and parent information sheets will be available. Research staff and clinicians from the Neonatal Intensive Care Unit will be able to recruit a whānau into the study, most commonly this will be the bedside nurse.

# Engagement and Responsiveness with Māori

This protocol was developed in consultation with [name], whose third child was born prematurely, and required PIVCs during her hospitalisation. [name] identifies as Māori (Raukawa, Ngāpuhi) and is a Steering Group Member. [name] will assist with ongoing Māori engagement, and ensure that study processes are culturally appropriate. Additionally, [name] will continue to provide cultural support to the research team.

[name] (Raukawa, Ngāpuhi) and [name] (Tarawhiti) who is the Social Worker within the Neonatal Intensive Care Unit at Waikato Hospital, developed both the name and logo for the project. The Pēpi Splint project has been reviewed by the Manager of Māori Health at Waikato District Health Board and received support.

At Wellington Regional Hospital the Whānau Care Services Manager [name] (Manager – Capability Māori Health Development Group, Chairperson of the Research Advisory Group Māori) has reviewed the project and was supportive. In addition, a formal application for the Pēpi Splint Project has been made to RAG-M.

We require 30 babies to participate. Within Wellington Regional Hospital 20% of the admitted babies are identified as being of Māori ethnicity. We hope to be able to recruit at least 6 Māori babies. Due to the small numbers of babies required for this initial phase of the project we will be unable to determine any similarities between Māori and non-Māori babies.

## Data collection, Management and Analysis

Data will be collected into Case Report Forms (CRFs) which will be held at the bedside during the study period.

#### Retention

If a participant withdraws from the study, consent will be sought to use the data collected up to the point of withdrawal.

## Data management

Data will be checked for logic errors by the research nurse. All data will be independently electronically entered by two investigators and later compared for agreement. Variations between data entries will be compared and discussed.

#### Statistical methods

Statistical analysis will be performed with JMP v14 and R v 3.61.

#### Descriptive Analyses

Categorical data will be presented as number and percent and continuous data will be presented as mean, standard deviation or median and inter-quartile range, as appropriate. Count data will be presented as median and inter quartile range. Denominators will be given for all outcomes

### Primary Analyses

For the splint to be considered for use in clinical care we need to know if it will hold the intravenous catheter in place and whether skin damage or irritation occurs.

Two exact 95% confidence intervals will be calculated, one for the proportion of babies in which the Pēpi Splint was judged by the clinical team to have supported the PIVC, and one for the proportion of babies who experience an adverse event. Secondary outcomes will be to determine the acceptability of the Pēpi Splint to both parents and clinical staff.

### Monitoring

### Safety Monitoring.

A Safety Monitoring (harms) procedure has been established. The Safety Monitor will advise the Steering Committee. A Data Monitoring Committee (DMC) has not been established for the Proof of Concept study. However, if we proceed to a randomised controlled trial a DMC will be established.

#### Harms

An adverse event will be skin damage attributed to the use of the Pēpi Splint by the senior clinician within the Neonatal Intensive Care Unit. If skin damage is considered to be caused by the Pēpi Splint (skin irritation or injury or pressure areas) the splint will be removed, and appropriate clinical care will be provided by the clinical team. Standardised photos will be taken of any injury and forwarded along with the report for review by the Safety Committee within 24 hours. The Safety Committee will review and report back to the Steering Committee.

Extravasation/infiltration injury occurs when the PIVC migrates from the vein into tissues. This is a common injury caused largely by the fragility of the babies' veins and necessary medications and fluids. We will collect the number of babies who have extravasation injuries. However, as these injuries are common in the NICU this injury will not be an endpoint. If we proceed to a randomised controlled trial, we could include extravasation/infiltration injury as a secondary outcome.

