### **PICOT**

Participants	Neonates ≥30 weeks' gestational age, > 1000 g and admitted to the Neonatal Intensive Care Unit whom require an intravenous catheter.
Intervention	Application of the Pēpi Splint.
Control	Not required.
Primary outcome	The Pēpi Splint is effective and does not cause harm as
	measured by the bedside clinician
Planned sample size	30 babies
Timing of assessment	Assessment for the primary outcome will be for the duration that
	the Pēpi Splint remains on the baby.

Methods: Participants, Interventions

Study setting Neonatal Intensive Care Unit at Wellington Regional Hospital

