### **Outcomes**

# Primary Outcome

The proportion of babies in which the Pēpi Splint was determined by the bedside nurse to have supported the secured the PIVC for the required time. The proportion of babies who experience an adverse event related to the Pēpi Splint.

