### Sample size

The primary reason for this Proof of Concept phase is to determine if the Pēpi Splint will support the PIVC and any adverse events related to the use of Pēpi Splint.

We do not expect any adverse events. We have determined that using a sample size of 30 where no adverse events have been observed, we can be assured that the 95% upper band on the rate of adverse events will be less than 10% (3/30 = 0.1). This will provide enough evidence to justify the progression to a randomised controlled trial.

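### The only safety count is skin damage that one clinician attributes to the splint without written criteria; a count of all splint-site skin damage should stand beside it

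*Protocol*

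**What the plan says.** The safety half of the primary outcome (Protocol, Primary Outcome) is: "The proportion of babies who experience an adverse event related to the Pēpi Splint". The Harms section fixes what counts: "An adverse event will be skin damage attributed to the use of the" Pēpi Splint, with the unit's senior clinician making the attribution. It names irritation, injury and pressure areas as forms of such damage. It gives no criteria for attribution.

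Two other places describe the measurement differently:

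- Primary Analyses introduces the analysis by saying the investigators need to learn "whether skin damage or irritation occurs". It then specifies an exact 95% confidence interval for the proportion of babies with an adverse event, that is, the attributed event. Whether the interval is one- or two-sided is not stated.
- The PICOT table says that effectiveness and absence of harm are "measured by the bedside clinician", not by the senior clinician.

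The Sample size section sets the expectation, "We do not expect any adverse events", and then treats 0/30, with an upper bound below 10%, as sufficient evidence to go on to a randomised trial.

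**The concern.** Attributed damage is a subset of the damage that occurs. If the question is what occurs under the splint, a count passed through a causal judgement can only be equal or lower.

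The protocol's own setting makes that judgement hard. It describes neonatal skin injury as multifactorial and says tapes can cause pressure areas (Background and rationale). It expects most babies to have had an earlier catheter (Recruitment; Enrolment). There is no control arm, the device is visible, and the planned photos are taken after application and after removal (Images), so no pre-application skin photo is listed. Damage judged to come from tape, the catheter or an earlier site has no stated route into the primary analysis.

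At stake is the progression argument, which rests on a zero. With 30 babies, one classification decides whether that zero stands.

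**Working it through.** **Inputs.** n = 30 babies and 0 expected events (Sample size); an exact 95% interval for the adverse-event proportion (Primary Analyses); events counted only if attributed (Harms).

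**1. The plan's own figure.** The Sample size section says "the 95% upper band on the rate of adverse events will be less than 10% (3/30 = 0.1".

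- Rule of three: 3/30 = 10.0%.
- Exact one-sided 95% bound at 0/30: 1 − 0.05^(1/30) = 9.50%.
- Exact two-sided 95% limit at 0/30: 1 − 0.025^(1/30) = 11.57%.

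The stated figure reproduces on the one-sided reading.

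**2. What one more counted baby does.** The exact upper limit for x events is the p that solves P(X ≤ x | 30, p) = 0.05 (one-sided) or 0.025 (two-sided).

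| Babies counted | One-sided 95% upper | Two-sided 95% upper |
|---|---|---|
| 0/30 | 9.5% | 11.6% |
| 1/30 | 14.9% | 17.2% |
| 2/30 | 19.5% | 22.1% |
| 3/30 | 23.9% | 26.5% |

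On the scale on which the plan's figure holds, a bound below 10% is available at 0/30 and lost at 1/30.

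**3. How easily a zero can arise.** Let p be the true proportion of babies with any splint-site skin damage and s the probability that such damage is attributed to the splint. With babies independent, P(zero counted) = (1 − p·s)^30. The protocol gives neither p nor s, so both are assumptions, shown over a range.

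| p | s = 1 | s = 0.75 | s = 0.5 | s = 0.25 |
|---|---|---|---|---|
| 5% | 21.5% | 31.8% | 46.8% | 68.6% |
| 10% | 4.2% | 9.6% | 21.5% | 46.8% |
| 20% | 0.1% | 0.8% | 4.2% | 21.5% |

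Example: p = 10%, s = 0.5 gives (1 − 0.05)^30 = 0.95^30 = 21.5%, against 0.90^30 = 4.2% with full attribution. The table shows how far a zero attributed count can differ from zero occurrence. It does not say how much of the unattributed damage was wrongly discounted.

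**The case against.** The strongest defence is that the outcome is causal by design. The specific aims and the PICOT table both speak of the splint not causing harm, and the Primary Outcome asks for events related to the splint. Harms then puts this into practice, and only one introductory sentence in Primary Analyses speaks of occurrence. This stands as far as it goes: an attributed count is legitimate and should stay.

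Several stronger readings are tempting, but the protocol does not support them:

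- **The error runs only toward safety.** This holds only when the count is used as a measure of all-cause occurrence. For splint-caused damage, misattribution can go either way: a cautious clinician might blame a new device for marks left by earlier tape.
- **Nothing checks the judgement.** Harms sends standardised photos of any injury and a report to the Safety Committee within 24 hours, and exit photos are planned. This is partial mitigation. The committee has no stated power to reclassify an event, and the report is described after damage already considered splint-caused.
- **Irritation is left out.** It is within the definition once attributed; attribution removes events, not the type of damage.
- **Restricting events to skin contradicts the Primary Outcome.** Harms can be read as defining the term used there.
- **One baby always moves the result across 10%.** This is true only one-sided. Two-sided, 0/30 already gives 11.6%; sidedness is a separate matter.

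The two assessors can also be read as two steps, with the bedside clinician observing and the senior clinician attributing. That is plausible, but the protocol does not say so. Finally, the senior clinician's knowledge that every baby wears the splint is inferred from the single-arm design, since blinding is not mentioned.

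**Conclusion.** The point holds in a limited form. The safety co-primary relies on one attribution, made without written criteria, as its only count. One section frames the need as occurrence, another names a different assessor, and progression is argued from zero events. The count can therefore understate what occurs at the splint site, and a single baby left out separates an upper bound of 9.5% from 14.9% one-sided, or 11.6% from 17.2% two-sided.

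These are consequences per baby, not an estimate of bias. The size of any bias cannot be computed, because the protocol gives no rate of unattributed damage. The finding supports adding a second count and reconciling the text. It does not support replacing the attributed outcome or concluding that the trial is bound to look safe.

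**What to change.** Keep the attributed count. Beside it, report with its own exact 95% interval the proportion of babies with any skin damage, irritation or pressure area under or in contact with the splint, whatever the presumed cause. Exclude extravasation and infiltration, which stay a separate count as Harms already provides; without that exclusion a common injury that the protocol deliberately keeps out of the endpoint would enter it.

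Base the all-cause count on the bedside clinician's routine skin observations and the exit photos. Include the skin state noted before application, so that existing marks can be told from new ones. State that progression will be interpreted on both counts.

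Use one definition, and say who observes and who attributes, in PICOT, Primary Outcome, Primary Analyses and Harms.

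Cost: the observations and exit photos are already planned, so the change is wording plus one explicit pre-application skin entry on the data collection sheet. The all-cause count may exceed zero and will include some damage not due to the splint, so the figure may be less favourable.

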### **Ethics and Dissemination**

### Research ethics approval

National ethics approval will be obtained from the Health and Disability Ethics Committee (HDEC) prior to commencement.

#### Locality Approval

Institutional approval will be obtained from Capital and Coast District Health Board (CCDHB) prior to commencement at that site.

#### Protocol Amendments

All amendments to the final version of this protocol will require review and approval of the Steering Committee, and will be submitted to HDEC and DHB Research Offices, as appropriate. All amendments, including approval date, will be recorded with this protocol.

### Consent

All parents identified will be given a parent information sheet, followed by a discussion with a member of the clinical team. Written informed consent will be sought. A copy of the consent form will be kept with the baby's notes and a copy given to the parents. Babies will be enrolled in the study following informed consent prior to the peripheral intravenous catheter being placed.

### Withdrawal from the Study

Parents will be able to discontinue participation in the study at any time. If parents do choose to withdraw, we will seek permission to include all data collected in analysis. If parents do not want their data to be included in the analysis, all data will be returned to the whānau.

#### Enrolment

It is expected that babies will be enrolled following admission to the Neonatal Intensive Care Unit. It is likely that most babies will have previously had an PIVC for treatment or fluids. A clinician (nurse or doctor) who has attended education sessions about the Pēpi Splint Project will be able to enrol a baby (whānau) into the study.

### Confidentiality

Healthcare professionals involved in the care of babies in the Neonatal Intensive Care unit will identify eligible families. All data collected including NHI number, entry criteria met, and the signed consent form will be held by the principal investigator in a locked office and on a password protected computer. All data collected about families whose babies are not ultimately recruited to the study will be destroyed, although signed consent forms will be retained.

Access to health information collected during the study will be limited to recruitment staff. A secure database will hold any identifiable data separately from the trial data and access to this will be limited to the investigators. Only a study number will identify all study data.

All participant research data and study records will be retained and stored for 10 years after the child has turned 16 years old.

At the completion of the study, all electronic data will be permanently digitally archived within the Victoria University of Wellington for archiving and data sharing according to international best practice.

#### Declaration of Interests

Investigators will declare any financial, intellectual or other potential conflicts of interest, as outlined by the International Committee of Medical Journal Editors (ICMJE), to the Steering Committee . The Steering Committee will decide on how any conflicts of interest are to be managed.

## Access to Data

The Steering Committee will have access to the full de-identified dataset and oversee analysis, interpretation and reporting of results. Approval will be sought from the Steering Committee prior to publication of study data. Care will be taken to avoid duplication in reporting of results.

#### Dissemination Policy

Results of the study will be presented at relevant conferences and published in a peer-reviewed scientific journal.

## Authorship policy

The Council of Science Editors standards for authorship will be applied. The Steering Committee will be responsible for planning manuscripts and resolving authorship disputes. Investigators and study personnel who do meet the criteria for authorship will be acknowledged as non-author contributors.

# Study Management

### Steering Committee

The Steering Committee will take overall responsibility for all aspects of the study, meetings will be held monthly or more frequently if required. Matters arising between meetings may be dealt with by email. The Principal Investigator will be responsible for maintaining a record of correspondence and minutes of meetings.

## Site Investigators

The Site Investigators who will have overall responsibility for satisfying local governance requirements, recruitment, assessments, data collection and integrity. They will be supported by the principal investigator and research nurse.

#### Finance and Insurance

This is a non-commercial study, participants in New Zealand will be covered by provisions of Accident Compensation Commission .

## **Significance**

If the Proof-of-Concept trial shows that the Pēpi Splint is effective and acceptable to both clinical staff and parents, then we will have data to proceed to a randomised controlled trial. The Pēpi Splint has the potential to reduce the incidence of iatrogenic skin injuries in babies compared to current standard practice, thus decreasing harm, reducing pain and improving the outcomes for hospitalised babies and their whanau.

#### **Timeline**

1 III I CIII I C	
2017	Completion of the development phase
	Report back to the senior clinical team
	Report to Health and Disability Commissioner about the
	development of the Pēpi Splint
10 May 2018	Patency gained Pēpi Splint (PCT/NZ2019/0050052).
December 2018	Waikato Māori Consultation and Protocol Development
July 2019	Proof-of-concept project development
	Consultation with Senior NICU Clinical Team at Waikato Hospital –
	Approval to proceed gained.
July 2019	Establishment of the Safety Officer (Committee)
September 2019	Health and Disability Ethics Committee application
	Pēpi Splint Available
December 2019	Health and Disability Ethics Committee - Declined
March 2020	Reapplication to the Health and Disability Ethics Committee
March 2020	Reapplication to the Regional Research Advisory Group Māori
	(RAG-M) and Child Health Committee
May 2020	Recruitment commence
October 2020	Review of Findings and Report to the Clinical team
November 2020	Dissemination of findings to families and the Perinatal community

### **Budget justification**

We estimate that we will need a Research Assistant/Nurse for 4 hours/baby. We require a Grade 2 Neonatal nurse grade Key tasks for the Research Nurse include

- Recruitment of families to the study
   Data collection and ensuring that all data collection sheets are completed and entered electronically.
- Administration Organising meetings and taking minutes for the Steering Group Committee
- Assisting with education to the Neonatal Intensive Care Unit Staff about the project.

Research Assistant/Nurse to work 4 hours/baby, s/he is paid 39.95/hour = (4 [contact]) x 30 = 4.794.00

All Pēpi Splints will be provided by Mike Williams Design Limited. The camera has been provided by the Faculty of Health for the duration of the data collection period.

